#### 2.1 PROTOCOL SYNOPSIS

The Protocol Synopsis is in Appendix 1.

#### 2.2 DETERMINATION OF SAMPLE SIZE

Patients will be randomly allocated in a 3:2 ratio to the implant arm or intravitreal arm.

The primary endpoint is the change in BCVA score from baseline averaged over Weeks 36 and 40. The study is sized to achieve adequate power to show non-inferiority (NI) and equivalence of the implant arm to the intravitreal arm in the change in BCVA score from baseline averaged over Week 36 and Week 40 using an NI margin of 4.5 letters and equivalence margins of  $\pm 4.5$  letters.

Assuming a standard deviation of 9.5 letters for the change from baseline in BCVA score averaged over 36 and 40 weeks, up to a true mean change from baseline in BCVA of 0.75 letters worse for the PDS 100 mg/ml arm, compared with the monthly intravitreal arm, 216 patients in the implant arm and 144 patients in the intravitreal arm will provide at least 90% power to demonstrate NI and equivalence between the two treatment groups. Calculations were based on a one-sided *t*-test at  $\alpha$ =0.025 level for the NI test and two one-sided *t*-tests at the  $\alpha$ =0.025 level for the equivalence test with the assumption of a 10% dropout rate by Week 40 and a 10% increase for the trimmed mean analysis. Note, the original sample size did not account for the type I error adjustment specified in Section 3.2, however the study will still have at least 90% power with this adjustment.

An independent statistician from the Independent Data Coordinating Center (iDCC) was employed to conduct a masked evaluation of the variance of the primary efficacy endpoint, but not the proportion of patients who receive supplemental treatment during the study or the study dropout rate before the end of enrollment because the enrollment was too rapid for these evaluations to be of value. The variance comparison to the assumptions used in planning the study did not suggest the initial assumption for the variance of the primary efficacy endpoint was substantially lower. Therefore, no change to the planned sample size was required. However, independent of this assessment, due to a high speed of enrollment combined with a lower screen failure rate than expected, there were a total of 418 patients enrolled. Details of the masked assessment and findings are provided in the memorandum from the iDCC in Appendix 4.

#### 2.3 ANALYSIS TIMING

The primary analysis will be performed when all patients have completed the Week 40 visit or have discontinued from the study prior to Week 40, all data collected through Week 40 are in the database, and the data have been cleaned and verified. At the time of the primary analysis, the study will be ongoing. An analysis of the available data post Week 40 (after Week 40 and up to a specified clinical cutoff date) will also be performed. Such results will be reported with, but separate from, the 40-week study results to provide additional information.

Additional analyses may be performed to support the requirements of health authorities relative to marketing applications, as appropriate.

The final analysis will be performed when all patients have either completed the 2-year study period (i.e., Week 96) or discontinued early from the study, all data from the study are in the database, and the database is locked.

# 3. STUDY CONDUCT

#### 3.1 RANDOMIZATION

Patients will be randomly allocated in a 3:2 ratio so that approximately 216 patients will receive the PDS implant with 100 mg/mL ranibizumab Q24W and approximately 144 patients will receive Q4W intravitreal injections of 10 mg/mL ranibizumab. On the day of a patient's randomization visit, BCVA will be measured based upon the ETDRS chart assessment at a starting test distance of 4 meters and randomization will be stratified by the BCVA score (<74 letters vs.≥74 letters). Randomization will be performed through an IxRS.

#### 3.2 INDEPENDENT IMAGE READING CENTER

All ocular images will be obtained by trained and certified site personnel at the study sites and forwarded to the central reading center for independent, masked, analyses and storage.

#### 3.3 DATA MONITORING

An independent Data Monitoring Committee (iDMC) will monitor safety and study conduct on an ongoing basis. Members of the iDMC will be external to the Sponsor and will follow a charter that outlines the iDMC's roles and responsibilities. The iDMC will meet approximately every 6 months (frequency adjustable as required) to evaluate unmasked ocular and systemic (non-ocular) safety events. After reviewing the data, the iDMC will provide a recommendation to the Sponsor as described in the iDMC Charter. Final decisions will rest with the Sponsor. Any outcomes of these data reviews that affect study conduct will be communicated in a timely manner to the investigators for notification of their respective Institutional Review Boards (IRBs).

A nominal type I error penalty of 0.0001 will be taken for each time the iDMC reviews unmasked data prior to the formal analysis of the primary efficacy endpoint. At the time of the primary analysis, it is estimated that 3 interim data reviews will have been conducted by the iDMC; therefore, efficacy analyses will be performed with a family-wise significance level of 0.0497.

#### 4. STATISTICAL METHODS

Descriptive summaries will include the mean, standard deviation, median, and range for continuous variables, and counts and percentages for categorical variables.

#### 4.1 ANALYSIS POPULATIONS

## 4.1.1 Efficacy Population

Efficacy data will be summarized for the Efficacy Population comprising all patients who are randomized and receive the study treatment, with patients grouped according to treatment actually received (patients who receive PDS implant will be included in the PDS 100 mg/ml group).

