# 6.2 SUMMARIES OF CONDUCT OF STUDY

Patient disposition (the number of patients randomized, treated, and completing each study period) will be tabulated by treatment received. Reasons for premature study treatment discontinuation and study discontinuation, any eligibility criteria deviation, and other major protocol deviations will also be tabulated.

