## 6.4 EFFICACY ANALYSES

Efficacy data will be summarized on the efficacy population comprising all patients who are randomized and receive the study treatment, with patients grouped according to treatment actually received. Patients who received the PDS implant will be included in the implant arm.

Unless otherwise noted, analyses of efficacy outcome measures will be stratified by baseline BCVA (<74 letters vs.  $\geq$ 74 letters). The stratification factor as recorded in IxRS will be used. The estimates and confidence intervals (CIs) will be provided for the mean

(for continuous variables) or proportion (for binary variables) for each treatment group and the difference in means or proportions between two treatment groups. All CIs will be two-sided and at the 95.03% level. Details of the calculation of the estimates and CIs will be provided in the SAP.

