Continuous delivery of ranibizumab from the implant, with a prolonged fixed period between refill-exchange intervals, is a novel approach that may result in less-frequent need for treatment than monthly dosing and patient monitoring, while maintaining optimal visual outcomes. The Phases I and II PDS studies provided evidence of the safety and tolerability of the PDS and support the evaluation of the PDS in a Phase III study.

The purpose of this document is to provide details of the planned analyses for Study GR40548 (Archway). The analyses and endpoints specified in this document supersede the analysis plan described in the study protocol and the previous version of the Statistical Analysis Plan (SAP).

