#### 4.1.2 Per-Protocol Population

A per protocol analysis is planned as a sensitivity analysis for the primary endpoint and the key secondary endpoint. Prior to study unblinding, protocol deviations will be reviewed and a determination of the definition of the population for per protocol analysis will be made.

The Per-Protocol Population is defined as all patients in the Efficacy Population who do not have a major protocol deviation that impact the efficacy evaluation. For analyses based on this patient population, patients will be grouped according to the treatment actually received.

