#### 4.2 ANALYSIS OF STUDY CONDUCT

Patient disposition (the number of patients randomized, treated, and completing each study period) will be tabulated by treatment actually received in Efficacy Population. Reasons for premature study treatment discontinuation and study discontinuation will be tabulated and a listing will be provided. Detailed, free text reasons are collected for discontinuations due to physician decision and 'other' reasons. This information will be included in the listing.

Eligibility criteria deviation and other major protocol deviations will be tabulated and a listing will be provided.

Exposure to study treatment (number of study treatments [PDS refill-exchanges, intravitreal ranibizumab injection, supplemental intravitreal ranibizumab injection] and duration of treatment) will be summarized by treatment group for the study eye in the Safety Population.

Duration of treatment is the time from first study treatment (implant or intravitreal ranibizumab injection) to the earlier of:

- The date of treatment discontinuation or date of study completion
- The analysis cutoff date

Pre-treatment and concomitant systemic medications, ocular medications for the fellow eye and, ocular medications for the study eye will be summarized separately by treatment group. Measures were implemented to mitigate the risk to data integrity posed by coronavirus disease 2019 (COVID-19). The impact of COVID-19 will be assessed in the COVID-19 Clinical Study Report (CSR) Annex in terms of the following criteria:

- Early study treatment discontinuation due to COVID-19
- Missed treatments due to COVID-19 or related precautions
- Use of prohibited therapy due to COVID-19
- Missing BCVA or BCVA not performed per protocol due to COVID-19 or related precautions

- Major protocol deviations associated with COVID-19 directly or indirectly
- Missed visits reported as due to COVID-19 or related precautions
- Early study discontinuation due to COVID-19
- Death due to COVID-19
- Confirmed or suspected cases of COVID-19 and adverse events (AEs) associated with COVID-19

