#### 4.4 EFFICACY ANALYSIS

The efficacy analyses will be based on the Efficacy Population.

Patients in the PDS 100 mg/mL arm can receive intravitreal ranibizumab injection as supplemental treatment if they meet the criteria described in Section 2.

Unless otherwise noted, analyses of efficacy outcome measures will be stratified by baseline BCVA (<74 letters vs.≥74 letters). The stratification factor as recorded in IxRS will be used. The estimates and confidence intervals (CIs) will be provided for the mean (for continuous variables) or proportion (for binary variables) for each treatment group and the difference in means or proportions between two treatment groups. All CIs will be two-sided and at the 95.03% level (see Section 3.3).

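### The SAP disposition table counts randomized patients only within the treated Efficacy Population, so randomized-but-untreated patients are not shown by assigned arm.

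*SAP*

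**What the plan says.** SAP 4.1.1 defines the Efficacy Population as "comprising all patients who are randomized and receive the study treatment, with patients grouped according to treatment actually received". SAP 4.4 adds: "The efficacy analyses will be based on the Efficacy Population". Protocol 6.4 has the same definition and states: "Patients who received the PDS implant will be included in the implant arm".

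The sensitivity sets sit inside this one. The Per-Protocol Population (SAP 4.1.2) is drawn from the Efficacy Population, and in it "patients will be grouped according to the treatment actually received". The complete-case analyses in SAP 4.4.2.1 are drawn in turn from the Per-Protocol Population.

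On disposition, SAP 4.2 says: "Patient disposition (the number of patients randomized, treated, and completing each study period) will be tabulated by treatment actually received in Efficacy Population". It continues: "Reasons for premature study treatment discontinuation and study discontinuation will be tabulated and a listing will be provided". That second sentence names no population. Protocol 6.2 has a similar line without the Efficacy Population restriction: "Patient disposition (the number of patients randomized, treated, and completing each study period) will be tabulated by treatment received". SAP section 1 settles which document governs: "The analyses and endpoints specified in this document supersede the analysis plan described in the study protocol".

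**The concern.** A patient must be treated to enter the Efficacy Population. A table of randomized patients limited to that population therefore cannot show anyone who was randomized and not treated. Grouping by treatment received also gives such a patient no column.

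This matters more here than in a masked drug trial, because the two arms reach first treatment differently. Under SAP section 2, intravitreal patients are injected at the end of the randomization visit and implant patients have surgery 1 to 7 days later. Protocol 3.1 leaves patients and sites unmasked. Protocol 4.4.1 requires implant patients on aspirin or NSAIDs to interrupt them before surgery, and Protocol 3.1 foresees surgery missing its window. Loss after randomization that differs by arm is not protected by randomization, and in a non-inferiority trial readers will want to see it by arm with reasons.

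**Working it through.** **Reading the passages together**

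1. Efficacy Population = randomized and treated, grouped as treated (SAP 4.1.1).
2. Disposition table = numbers randomized, treated and completing, within that population, by treatment received (SAP 4.2).
3. From 1 and 2, randomized = treated in every column.
4. Protocol 6.2 does not repair this. It also groups by treatment received, and the SAP supersedes it.
5. The primary estimand (SAP 4.4.1) lists four intercurrent events. Never starting treatment is not one of them, so these patients leave through the population definition without a stated handling rule.
6. What can still be recovered: SAP 2.2 reports 418 enrolled, which I take to mean randomized. 418 minus the Efficacy Population size gives the total untreated, but not the split by arm.

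**The plan's own figures**

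- Significance level (SAP 3.3): 0.05 − 3 × 0.0001 = 0.0497, or 0.02485 one-sided. This agrees with the SAP.
- Power (SAP 2.2): 216 + 144 patients, SD 9.5, true difference −0.75, margin 4.5, one-sided 0.025. Allowing 10% for dropout and 10% for trimming leaves 216 × 0.81 = 175 and 144 × 0.81 = 116.6. A noncentral-t calculation gives 90.9% for non-inferiority and 90.4% for equivalence, in agreement with the stated 90%.

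**How much could untreated patients matter?**

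The documents give neither a count nor an outcome for these patients, so what follows is assumption.

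*Room at planning values.* A 3:2 split of 418 is about 251 and 167. After 10% dropout this is 226 and 150.

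- SE = 9.5 × √(1/226 + 1/150) = 1.00
- Half-width = 1.969 × 1.00 = 1.97
- Lower limit at an observed −0.75 = −0.75 − 1.97 = −2.72
- Room = 4.5 − 2.72 = 1.78 letters; for the 3.9-letter margin of SAP 4.4.2.1, 3.9 − 2.72 = 1.18 letters

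*Shift.* Suppose k of 251 implant-assigned patients are untreated and average D letters worse than treated implant patients, with no untreated controls. Including them moves the difference by k/251 × D. D runs from 0 to 15; the 15 is borrowed from the individual supplemental-treatment criterion in Protocol 5.1.5.3 and is a severe value for a group mean.

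| k (assumed) | % of 251 | Shift, D = 0 to 15 | D that uses up 1.78 | D that uses up 1.18 |
|---|---|---|---|---|
| 3 | 1.2 | 0 to 0.18 | 149 | 99 |
| 7 | 2.8 | 0 to 0.42 | 64 | 42 |
| 13 | 5.2 | 0 to 0.78 | 34 | 23 |

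Untreated controls offset this. With 13 implant and 2 control patients at D = 15, (13/251 − 2/167) × 15 = 0.60.

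*Count that would reach the limit at D = 15.* 1.78/15 × 251 = 29.8, so 30 patients (margin 4.5); 1.18/15 × 251 = 19.7, so 20 (margin 3.9).

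*A less favourable result.* At an assumed observed −1.5 the room is 4.5 − 3.47 = 1.03 and 3.9 − 3.47 = 0.43. At D = 15 the counts are 1.03/15 × 251 = 17.2, so 18, and 0.43/15 × 251 = 7.2, so 8.

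*Weeks 88/92.* Dropout is not given. At an assumed 20% to 30% and an observed −0.75, the room under the 3.9-letter margin is 1.06 to 0.92 letters, and 13 untreated patients would need D of 20.5 to 17.7.

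Throughout, the half-width is held fixed and no imputation variance is added.

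**The case against.** The strongest reply has four parts.

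- **The imbalance is not documented.** Only the schedule supports it. Protocol 4.1.1.1 requires willingness to attend all visits, Protocol 3.1 allows randomization assessments to be repeated, and Protocol 4.4.1 has medication interruptions planned at screening. All of these limit exit before surgery. This stands: the imbalance is an inference.
- **The restriction may be loose drafting.** SAP 4.2 lists randomized and treated as separate counts, which is pointless if they must be equal. The discontinuation and deviation tables name no population, and Protocol 4.6.2 has withdrawal reasons recorded. This narrows the gap, but no table is committed to untreated counts and reasons by assigned arm, and a programmer following the SAP would produce the uninformative version.
- **A different population would hardly change the model.** The MMRM uses post-baseline change, so a patient without post-baseline BCVA adds nothing whichever set is named. This stands, and it is why the table matters more than a rerun.
- **The Primary and Update CSRs were complete before this SAP version.** They may already show these patients; that cannot be known from the documents.

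A reader might infer that the primary result is biased in favour of the implant, or that non-inferiority is at risk. The documents support neither. There is no untreated count, the direction could be nil or reversed, and the calculation shows no changed conclusion at planning values.

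**Conclusion.** The disposition table is wrong as written: it reports a randomized count that can only equal the treated count. That follows from the SAP text alone and needs no assumption. All efficacy sets share the restriction and the as-treated grouping.

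Severity is minor. Assumed shifts of up to 0.78 letters stay inside the room of 1.78 and 1.18 letters at planning values. They exceed it only under a further assumption, such as an observed −1.5 against the 3.9-letter margin with at least 8 untreated implant patients averaging 15 letters worse. The numbers rest on a 3:2 split of 418, SD 9.5, 10% dropout, and counts and deficits chosen for illustration.

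One related wording is open. SAP 4.3, in defining baseline, counts an intravitreal injection after randomization as first study treatment. Protocol 4.3.2.2 lists the delayed-surgery injection separately from control-arm study treatment. An implant-assigned patient with only that injection could be read as belonging to the intravitreal group or as untreated. This is a clarification, not a second error.

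**What to change.** Keep the primary analysis and its population.

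1. In SAP 4.2, remove the Efficacy Population restriction. Tabulate disposition for all 418 randomized patients by IxRS-assigned arm, with counts and reasons for those randomized and not treated.
2. Add one supplementary analysis of the primary and key secondary endpoints, grouped by assigned arm and using all available post-baseline BCVA. If nobody received the other arm's treatment and no untreated patient has post-baseline BCVA, state that it equals the primary analysis instead of running it. Label it post hoc for Weeks 36/40 and 44/48; for Weeks 88/92 it can be specified before the Final CSR.
3. State in one phrase how the analysis groups an implant-assigned patient who had only the delayed-surgery injection.

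A tipping-point analysis is not warranted on these figures. The cost is one revised table on existing data and at most one extra supplementary run, with no new patients or visits.

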#### 4.1.2 Per-Protocol Population

A per protocol analysis is planned as a sensitivity analysis for the primary endpoint and the key secondary endpoint. Prior to study unblinding, protocol deviations will be reviewed and a determination of the definition of the population for per protocol analysis will be made.

The Per-Protocol Population is defined as all patients in the Efficacy Population who do not have a major protocol deviation that impact the efficacy evaluation. For analyses based on this patient population, patients will be grouped according to the treatment actually received.

#### 4.1.3 Pharmacokinetic Population

The PK population will be based on the subset of patients in the Safety Population with at least one post study treatment PK sample available.

# 4.1.4 Pharmacokinetic-Evaluable Population

The PK-Evaluable Population will consist of patients in the PK Population excluding patients receiving intravitreal injections of ranibizumab in the study eye post PDS implant (including supplemental treatment), patients with fellow eye ranibizumab or bevacizumab treatment, or prior bevacizumab treatment in either eye.

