• To evaluate the safety and tolerability of ranibizumab, delivered via the PDS Q24W with the 100-mg/mL formulation compared with that of 10- mg/mL (0.5-mg dose) Q4W intravitreal ranibizumab injections	
 
Incidence and severity of ocular and systemic (non-ocular) AEs
 
Incidence, severity, and duration of AESIs
 
Incidence, severity, and duration of ocular AESIs during the postoperative period (up to 37 days of initial implantation) and follow-up period (>37 days after implantation surgery)
 

Pharmacokinetic Objective	Corresponding Endpoints
• To characterize the serum pharmacokinetics of ranibizumab in patients after the initial fill and subsequent refill-exchanges in patients with the PDS	
 
Observed serum ranibizumab concentrations at specified timepoints
 
Additional estimated PK parameter values, including AUC0-6M, Cmax, Cmin, and t1/2 after PDS implant insertion
 

Exploratory Pharmacokinetic Objectives	Corresponding Endpoints
• To evaluate potential relationships between drug exposure and the efficacy of the PDS	
 
Relationship between serum concentration or PK parameters for ranibizumab delivered via the PDS and efficacy endpoints
 

To characterize ranibizumab aqueous     humor concentration over time	
 
Observed aqueous humor ranibizumab concentrations over time
 

Immunogenicity Objective	Corresponding Endpoint
• To investigate the formation of serum anti-ranibizumab antibodies	The incidence of ADAs during the study, grouped in the following manner:
	
 
Patients who were ADA negative at baseline and became positive only after dosing
 

	
 
Patients who were ADA positive at randomization and ADA titer increased after dosing
 

	
 
Patients who were ADA positive at randomization and ADA titer did not increase after dosing
 

Exploratory Biomarker Objectives	Corresponding Endpoints
• To explore relationships between aqueous humor free-VEGF concentrations over time and the efficacy of ranibizumab, delivered via the PDS Q24W with the 100-mg/mL formulation	
 
Comparison of patients with and without aqueous humor free-VEGF present between refill-exchanges and needing supplemental treatment
 
Comparison of patients with and without aqueous humor free-VEGF present between refill-exchanges and CST changes from bacaging over time
 

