#### 3.5.4 Rationale for Pharmacokinetic Sample Collection Schedule

The objective of the serum PK sampling is to characterize the serum pharmacokinetics of ranibizumab delivered via the PDS in the implant arm and to assess the potential impact of immunogenicity on pharmacokinetics. The serum pharmacokinetics of ranibizumab following intravitreal administration has been well characterized; however, the PK profile for continuous delivery is expected to be markedly different (by design).

In this study, PK serum samples will be collected from all patients at all sites at the randomization visit and at Weeks 4, 24, 36, and 96 to align with anti-drug antibody (ADA) sample collection timepoints. At selected sites, additional PK samples will be collected from patients in the implant arm on Days 2 and 7 and Weeks 12, 48, and 72. The sampling timepoints through Week 24 are expected to be sufficient to estimate the half-life for ranibizumab delivery from the implant, and sampling timepoints at Weeks 36–96 will be assessed to ensure consistent drug delivery over time. Limited PK sampling will occur in the intravitreal arm (control) because the serum pharmacokinetics of ranibizumab following intravitreal administration has been well characterized, as presented in the PDS Investigator's Brochure. In addition, at selected sites, a PK sample will be collected in patients in the intravitreal arm 1 to 5 days after an intravitreal ranibizumab 0.5 mg injection in order to collect a sample near  $C_{max}$ .

See Appendix 1 and Appendix 2 for sample collection timepoints.

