#### 3.5.6 Rationale for Biomarker Assessments

Previous studies have demonstrated a broad range of treatment needs across patients (Ho et al. 2014); thus, some patients in the implant arm may require additional treatment(s) with ranibizumab outside of the fixed 24-week dosing interval. To better understand the cause of their increased treatment needs, aqueous humor samples from patients who require supplemental treatment will be collected (just prior to the supplemental treatment and at the next subsequent visit) and analyzed for drug and/or free-VEGF concentrations and correlated with retreatment need. In addition, aqueous humor, plasma, and serum samples will be collected from patients who terminate study

treatment early or who undergo explantation. Information obtained from these analyses will be used in an effort to better understand variability in treatment need and to identify patients best suited for continuous delivery of ranibizumab.

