#### 4.1.5 Aqueous Humor Pharmacokinetic-Evaluable Population

The Aqueous Humor PK-Evaluable Population is the subset of patients in the PK-Evaluable Population with at least one optional aqueous-humor sample.

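### The PK-Evaluable Population drops a whole patient for any later non-PDS ranibizumab dose, so it discards pre-dose samples and makes early PK depend on later rescue; a sample-censored set should be added beside it

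*SAP*

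**What the plan says.** The PK objective in Protocol Table 1 is "To characterize the serum pharmacokinetics of ranibizumab in patients after the initial fill and subsequent refill-exchanges in patients with the PDS". The listed parameters include AUC over 6 months, Cmax, Cmin and half-life, and an exploratory objective relates exposure to efficacy. Protocol 3.5.4 adds that "sampling timepoints at Weeks 36–96 will be assessed to ensure consistent drug delivery over time".

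Three PK sets are defined in the SAP:

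- **PK Population (4.1.3):** the "subset of patients in the Safety Population with at least one post study treatment PK sample available". Nothing is removed for ranibizumab from another source.
- **PK-Evaluable Population (4.1.4):** the "PK Population excluding patients receiving intravitreal injections of ranibizumab in the study eye post PDS implant (including supplemental treatment"), and also without "patients with fellow eye ranibizumab or bevacizumab treatment, or prior bevacizumab treatment in either eye". There is no time limit and no rule at sample level.
- **Aqueous Humor PK-Evaluable Population (4.1.5):** members of the PK-Evaluable set "with at least one optional aqueous-humor sample".

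SAP 4.5 tabulates and plots serum concentrations for both serum sets. AUC, Cmax and half-life come from the intensively sampled implant patients, with no analysis set named. None is named for the exposure-efficacy work either. Protocol 6.6 treats the PK-Evaluable set as an optional sensitivity set. SAP Section 1 says the SAP replaces the protocol's analysis plan, and SAP 4.5 does not repeat that ranking.

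**The concern.** Rescue is a post-baseline event triggered by loss of acuity or retinal thickening from disease activity (Protocol 5.1.5.3). Removing a patient's entire record because of it makes the inclusion of early concentrations depend on a later outcome. The protocol itself thinks the two may be linked: "aqueous humor samples from patients who require supplemental treatment will be collected (just prior to the supplemental treatment and at the next subsequent visit"), and Protocol 3.5.6 plans to correlate the drug and free-VEGF results with the need for retreatment.

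If low delivery contributes to rescue, the restricted set loses part of its low tail. Delivery would then look more uniform over Weeks 36 to 96 than it is, and an exposure-efficacy analysis run in that set would lack the treatment failures. If rescue instead reflects greater need at normal delivery, the concentrations are not biased this way, but valid samples are still thrown away.

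The PK Population is not a full remedy. It keeps the pre-rescue samples but does not separate them from later samples that may carry supplemental or fellow-eye drug. The plan has no set containing exactly the samples drawn before other post-implant ranibizumab was given.

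**Working it through.** The plan gives no figure for the PK sets, so there is nothing of its own to reproduce.

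**Inputs**

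- Post-implant serum PK at all sites: Weeks 4, 24, 36, 96 (4 samples). Selected sites add Days 2 and 7 and Weeks 12, 48, 72 (9 in total). Source: Protocol 3.5.4.
- Supplemental treatment is possible only at Weeks 16, 20, 40, 44, 64, 68, 88 and 92. Source: Protocol 5.1.5.3.
- At a supplemental visit the serum PK sample is drawn before the injection. Source: Protocol Appendix 5.

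**Step 1: scheduled samples that precede the first supplemental dose**

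| First dose at Week | All sites | Selected sites | Kept by SAP 4.1.4 |
|---|---|---|---|
| 16 or 20 | 1 of 4 | 4 of 9 | 0 |
| 40 or 44 | 3 of 4 | 6 of 9 | 0 |
| 64 or 68 | 3 of 4 | 7 of 9 | 0 |
| 88 or 92 | 3 of 4 | 8 of 9 | 0 |

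The pre-injection serum sample at the first supplemental visit is a further pre-dose sample that is lost.

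**Step 2: what supplemental drug can reach in the PK Population**

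Days 2 and 7 and Weeks 4 and 12 precede Week 16, so they cannot contain it. Of the scheduled samples through Week 24, only Week 24 can, at a nominal 28 days (Week 20 dose) or 56 days (Week 16 dose). The documents give no serum half-life for an intravitreal dose. Assuming 3, 7 or 14 days, the residual is 0.5^(days / half-life):

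- 28 days: 0.2%, 6%, 25%
- 56 days: about 0%, 0.4%, 6%

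Fellow-eye ranibizumab is allowed at the investigator's discretion (Protocol 4.4.1) and can reach any timepoint.

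**Step 3: dose shares, as illustration**

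- One supplemental dose against one fill: 0.5 / 2.0 = 25%.
- Assumed monthly fellow-eye treatment over 24 weeks: 6 × 0.5 = 3.0 mg, and 3.0 / (3.0 + 2.0) = 60% of total dose.

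These are shares of dose, not of serum concentration.

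**Step 4: patients removed**

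Taking 3/5 of the 418 enrolled, 418 × 0.6 = 250.8, or about 251 implant patients. If 2% to 20% are ever supplemented (assumed), 250.8 × 0.02 ≈ 5 to 250.8 × 0.20 ≈ 50 are dropped for that reason alone.

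**Step 5: possible selection effect, under assumptions**

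Let the trough be lognormal with log-SD σ, let rescue occur in the fraction p with the highest latent need, and let ρ be the correlation of low log-trough with need. With k the normal quantile of 1 − p, the mean trough in the never-rescued divided by the overall mean is Φ(k + ρσ) / (1 − p).

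- Low end: p = 0.02, ρ = 0.3, CV 30% (σ = √ln 1.09 = 0.294). Φ(2.054 + 0.088) / 0.98 = 0.9839 / 0.98 = 1.004, so +0.4%.
- High end: p = 0.20, ρ = 0.7, CV 50% (σ = √ln 1.25 = 0.472). Φ(0.842 + 0.331) / 0.80 = 0.8795 / 0.80 = 1.099, so +10%.

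Simulation over the same ranges puts the rise in the 5th percentile at 0.7% to 24%. The values of p, ρ and CV are all assumed.

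**The case against.** An all-data set reported beside a restricted set is a normal pairing. SAP 4.5 shows individual and mean concentrations for both, so pre-rescue samples remain visible in the PK Population. A reader might infer that neither set characterises PDS delivery. The documents do not support that: the PK-Evaluable set describes delivery in patients with no other ranibizumab after implantation, and samples through Week 12 are free of supplemental drug in both sets.

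The illustrations can also be over-read. The 60% assumes monthly fellow-eye ranibizumab throughout, although any approved agent may be used and only if that eye needs treatment. It also counts the whole 2 mg fill as delivered, although a refill-exchange replaces what remains. The selection figures rest on an assumed link between trough and rescue. Protocol 3.5.6 speaks of a wide range of treatment needs and treats the cause of rescue as unknown. Nor can it be said that exposure-efficacy will be flattened, because no set is named for it.

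A reader might infer that the mandatory pre-rescue aqueous samples go unanalysed. They do not: the Biomarker Analysis Population (SAP 4.1.7) has no rescue exclusion, and SAP 4.6 analyses its data alongside ranibizumab PK.

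Finally, censoring after first rescue does not remove the selection at later weeks. All of this stands. It limits the claim and the remedy, but it does not justify discarding samples drawn before the dose that triggers exclusion.

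**Conclusion.** The concern holds as a defect of the restricted set. SAP 4.1.4 conditions early concentrations on later rescue or fellow-eye treatment and loses up to 3 of 4 (all sites) or 8 of 9 (selected sites) scheduled pre-dose serum samples per supplemented patient. SAP 4.1.5 inherits this and also requires an optional sample, so the only defined aqueous PK population omits the samples taken just before rescue in patients who then receive it.

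The sample counts follow from the documents. The size of any bias does not. A rise of 0.4% to 10% in the mean trough is what the assumed rescue rate, variability and correlation produce, and the direction itself needs low delivery to contribute to rescue. It would also be wrong to call every discarded early sample clean: all patients had intravitreal ranibizumab 21 to 28 days before Day 1 (Protocol 3.1), which may carry over into Days 2 and 7 in any set.

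The PK analysis is descriptive and no efficacy test depends on it. This is an inexpensive improvement, not a flaw in the trial's main conclusion.

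**What to change.** Keep the existing sets and add a sample-censored PK set. The Primary and Update CSRs are already complete, and SAP 4.5 allows further PK analyses, so adding is cleaner than replacing.

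- **Rule:** for each implant patient, keep serum samples up to and including the pre-dose sample at the first post-implant study-eye intravitreal ranibizumab dose or the first fellow-eye ranibizumab or bevacizumab dose, whichever is earlier. Exclude later samples. Retain the exclusions for prior bevacizumab and for a fellow eye already under such treatment.
- **Use:** name this set for Cmin, AUC, half-life and a supportive exposure-efficacy analysis, and report n per timepoint.
- **Aqueous samples:** summarise the mandatory pre-rescue drug concentrations in rescued patients separately from the scheduled optional samples. Pooling would mix outcome-triggered with scheduled sampling.

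The cost is SAP wording and a sample-level flag built from dosing dates already collected.

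Three downsides should be stated in the SAP. Fewer samples remain at later weeks. Censoring at rescue is still informative, because each rescue window precedes a Week 24, 48, 72 or 96 sample, so late-week summaries over-represent never-rescued patients. Possible carry-over from the pre-Day 1 injection into Days 2 and 7 is not addressed.
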